#### 6.2.4. Lille score

The Lille score is a tool that has historically been used to predict which subjects with severe AH (eg, screening Maddrey DF score  $\geq$  32) are not responding to corticosteroid therapy; usually after Study Day 7, and are potential candidates for alternative therapies {Louvet 2007}. The Lille score is calculated using baseline factors: age, albumin, total bilirubin, serum creatinine, prothrombin time; and the change in total bilirubin between baseline and Day 7 according to the following formula:

Lille score = Exp(-R)/[1+exp(-R)], where R = (3.19 - (0.101 × age [yrs]) + (1.47 × BL albumin [g/dL]) + (0.28215 × (BL total bilirubin [mg/dL] – Day 7 total bilirubin [mg/dL])) – (0.206 × RENAL INSUFFICIENCY) - (0.11115 × BL total bilirubin [mg/dL]) – (0.0096 × BL prothrombin time [seconds])

Renal insufficiency is rated 0 if absent and 1 if present (serum creatinine  $\leq 1.3$  or > 1.3 mg/dL, respectively). The result will be rounded to the nearest 0.001. Covance central laboratory data will be used to calculate Lille scores for a subject for analysis purposes except when 1 or more of the central values required to calculate the Lille score at Week 1 are missing and local laboratory data is available to calculate a Week 1 score. For these cases, local labs will be used to calculate all Lille scores for the subject. See Section 3.6.1 of this SAP for a complete description of imputations for Lille score for subjects in whom a Week 1 Lille score cannot be calculated based on central laboratory data.

Lille score will be summarized as a continuous variable by treatment group and visit at Weeks 1, 2, 3, and 4 by selecting the total bilirubin value for the subject and visit using the analysis visit windows specified in Section 3.8.2 of this SAP. An additional timepoint will be displayed for "Week 4 or last observation carried forward (LOCF)". For this additional timepoint, a subject will be included with their Week 4 analysis visit Lille score, or with the last chronologic Lille score collected between Study Days 2 and 24 for those subjects who have a missing Week 4 Lille score. The total bilirubin for the visit window will be substituted in place of the Day 7 total bilirubin value in the Lille score formula above to calculate the Lille score for Weeks 2, 3, and 4. The median (Q1, Q3) Lille score value at each on-treatment visit will be provided as a figure.

Lille score will additionally be summarized as a categorical variable at Week 1, Week 2, and at Week 4 (LOCF) by treatment group and visit for the following:

- 1) The number and percentage of subjects with a Lille response, defined as a Lille score < 0.45 (yes or no)
- 2) The number and percentage of subjects with a Lille null response, defined as a Lille score  $\geq 0.56$ , will be displayed by treatment group and visit. Null response is used as a criteria for premature discontinuation of prednisolone in clinical practice. Subjects with a complete or partial response (Lille score < 0.56) will be further subdivided into complete responders (Lille score < 0.16) and partial responders (Lille score 0.16 to < 0.56).

The denominator for the percentage calculation will be the number of subjects in the treatment group for the FAS or mITT analysis set (as appropriate). Subjects missing a Lille score value within the visit window will be counted as failures. Subjects with a calculated Lille score meeting non-responder or null-responder criteria will be summarized as "observed" failures. Subjects missing a value within the visit window will be summarized as "missing value". The reasons for subjects not having a Lille score will be summarized at each visit as follows:

- 1) Subjects who discontinue both study drugs in the regimen prior to the target day (ie, Study Days 7 [Week 1 and Week 4 LOCF] and Day 14 [Week 2] for the visit window will be summarized by the premature discontinuation reason for SEL/PLA from the study drug completion eCRF.
- 2) Subjects ongoing at the time of the visit will be summarize as "missing value at visit"

For the endpoints Lille response (yes, no) and Lille null response (vs. complete or partial response), p-values from a 2-sided Fisher's exact test will be presented for the Week 1 visit to explore whether there are differences between treatment groups.

A listing of the Lille scores included in analysis will be provided. A footnote will provide Subject IDs for those subjects who had Lille scores calculated using local laboratory data.

#### 6.2.5. Mortality Risk using Baseline MELD score and Lille Score at Day 7

A scoring system combining the Lille score at Day 7 and the baseline MELD score to calculate the 2- and 6-month overall mortality risk was created, and tested with a secondary derivation dataset (ie, validation dataset) {Louvet 2015}. The steps for calculating the mortality risk for an individual subject are described below:

Step 1: Calculate the mortality probability for an individual subject using the Lille score at Week 1 and baseline MELD scores from central laboratory data. Subjects with a missing centrally-assessed Lille score at Week 1 or baseline MELD score will utilize imputed values based on local laboratory data as specified in Section 3.6.1 of this SAP.

 $S = [2.4778 \times (Week \ 1 \ Lille \ score \ - \ 0.4114) + 0.0695 \times (Baseline \ MELD \ - \ 24.6812)] \times 0.9836$ 

where,

- 1) 0.4114 = mean value of Lille model in the secondary derivation dataset
- 2) 24.6812 = mean value of MELD score in the secondary derivation dataset
- 3) 0.9836 = the shrinkage factor estimated using bootstrap validation in the secondary derivation dataset
- 4) 2.4778 and 0.0695 = regression coefficients calculated from the multivariable prognostic model for the secondary derivation dataset

Step 2: Calculate mortality risk using S:

2-month mortality risk =  $[1-(0.8239^{exp(S)})]*100$ 

6-month mortality risk =  $[1-(0.7285^{exp(S)})]*100$ 

Where 0.8239 and 0.7285 were the survival rate at the mean values of predictors in secondary derivation dataset (calculated as the pooled survival estimates from cohorts included in secondary derivation dataset).

Numerical Example: a subject with Week 1 Lille score = 0.45 and a baseline MELD = 21:

Step 1: Calculate S =  $[2.4778 \times (0.45 - 0.4114) + 0.0695 \times (21 - 24.6812)] \times 0.9836 = -0.1576$ 

Step 2: Calculate the mortality risk using S

2-month mortality risk =  $[1-(0.8239^{exp(-0.1576)})]*100 = 15.3\%$ 

6-month mortality risk =  $[1-(0.7285^{exp(-0.1576)})]*100 = 23.7\%$ 

Mortality risk at Month 2 and at Month 6 will be provided as a continuous variable by treatment group.

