6.3.1. Week 1 Visit (±3 Days)

During the Week 1 safety visit the following will be performed and documented:

- Review of liver biopsy and central laboratory results if unavailable during the Screening or baseline period and reassess study entry criteria.
- Assess alcohol consumption
- Complete PE including, vital signs
- Assessments for HE, ascites, HRS, and infection
- Obtain blood samples for:
 - Hematology
 - Chemistry: ALT, AST, albumin, alkaline phosphatase, bicarbonate, BUN, calcium, chloride, creatinine, glucose, LDH, magnesium, phosphorus, potassium, sodium, total and direct bilirubin, total protein, uric acid, GGT. Samples should be drawn for central and local laboratory testing for calculation of the Lille Score (Section 6.9.12)
 - Coagulation Tests: PT, PTT, and INR.
 - Blood for Biomarkers
 - Sparse PK Sample
- Record all concomitant medications that the subject has taken since the previous visit
- Record any SAEs and all adverse events occurring since the previous visit
- Administer or dispense prednisolone, and provide subject with dosing instruction on appropriate dosing and administration.
- PPD
- Assess for study drug adherence

- Perform study drug accountability
- Calculate Lille Score at Week 1 based on local laboratory results (Section 6.9.12). If Lille score is ≥ 0.56 (null response), prednisolone treatment should be held. If Lille score is > 0.85, then both study drugs should be held. If the central lab results confirm Lille score stopping criteria has been met, the subject will be prematurely discontinued from study drug(s), as appropriate.

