6.9.12. Lille Score

The Lille score should be calculated at Day 7 using local laboratory results from Baseline/Day 1 (albumin, total bilirubin, creatinine, PT) and Week 1 (total bilirubin) for all subjects utilizing the following calculator (http://www.mdcalc.com/lille-model-alcoholic-hepatitis/), in appropriate units (SI or conventional).

Prednisolone should be discontinued in subjects with a Lille Score ≥ 0.56 at Day 7 (null response); these subjects may continue GS-4997/placebo treatment.

For safety monitoring of the stopping criteria of Lille score > 0.85, sites should also collect local laboratory results for total bilirubin at Weeks 2, 3, and 4 and use the same calculator to calculate the Lille Score compared to baseline values. When performing the calculation, ensure the Day 7 total bilirubin is changed to Week 2, 3, and 4 values at the appropriate time points.

If a subject's Lille score is > 0.85 at any time, they should stop both study drugs. If the central laboratory Lille score calculation is different from the local laboratory results, the stopping criteria will be based on central laboratory results.

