# 3.8.2. Analysis Visit Windows

Subject visits might not occur on protocol-specified days. Therefore, for purposes of analysis, observations will be assigned to visit windows.

In general, the baseline value will be the last nonmissing value on or prior to the first dose date of SEL/PLA study drug. When the Screening and Day 1 visits are conducted on the same date, the later time value for Covance laboratory values should be used for purposes of analysis since the date/time is prior to first dose date/time from the pharmacokinetic study drug administration (PKEX) eCRF for all 4 subjects (eg, Subject IDs PPD PPD and PPD PPD and PPD PPD

Analysis windows for efficacy measures of hepatic synthetic function (ie, ALT, AST, GGT, alkaline phosphatase, total bilirubin, direct bilirubin, albumin, INR, MELD, CPT, and Maddrey's DF), Lille score and recidivism to alcohol are displayed in column 2 of Table 3-1.

The analysis visit windows for liver fibrosis markers (ie, ELF score and its components) are displayed in the third column of Table 3-1.

The analysis visit windows for safety laboratory tests and vital signs will include laboratory values collected up to last dose date of any study drug + 7 days for "on-treatment" visit windows. Values that are collected  $\geq$  8 days after the last dose date of study regimen will be assigned to follow up visits, where FU day is defined as:

FU Day = Laboratory assessment date – Last Dose Date of Any Study Drug

For analyses of laboratory parameters that are both efficacy and safety variables (eg, hepatic synthetic function tests, and HbA1c), absolute value and change from baseline visit windows will be calculated from Study Day 1; while toxicity grading summaries will utilize safety analysis visit windows.

For all safety analyses related to laboratory toxicity grading, laboratory data collected up to 30 days after the date of last dose of any study drug will be included.

Visit windows for safety laboratory tests are displayed in the fourth column of Table 3-1.

Analysis Visit	Visit Windows for Hepatic Synthetic Function, Lille Scores, and Recidivism to Alcohol	Visit Windows for Liver Fibrosis Markers	Visit Windows for Vital Signs and Safety Laboratory tests (Hematology, Chemistry, Coagulation, and Lipids)
Baseline	Study $Day \le 1$	Study Day $\leq 1$	Study $Day \le 1$
Week 1	$2 \leq $ Study Day $\leq 10$	N/A	$2 \leq $ Study Day $\leq 10$
Week 2	$11 \leq $ Study Day $\leq 17$	N/A	$11 \leq $ Study Day $\leq 17$

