# **3.8.3.** Selection of Data in the Event of Multiple Records in an Analysis Visit Window

Depending on the statistical analysis method, single values may be required for each analysis window. For example, change from baseline by visit usually requires a single value, whereas a time-to-event analysis would not require 1 value per analysis window.

If multiple, valid nonmissing, continuous measurements exist in an analysis window, records will be chosen based on the following rules if a single value is needed:

• In general, the baseline value will be the last nonmissing value on or prior to the first dosing date of study drug, unless specified differently. If multiple measurements occur on the same day, the last nonmissing value prior to the time of first dosing of study drug will be

considered as the baseline value (ie, for Covance laboratory values). For measurements taken on the same date with visit names of screening and baseline (ie, for vital signs and ECGs), the baseline visit value will be utilized if available. If multiple measurements occur at the same time, the average of these measurements (for continuous data) will be considered the baseline value.

- For postbaseline visits:
  - The record closest to the nominal day (nominal day for Week  $X = (X \times 7)$  day) for that visit will be selected.
  - If there are 2 records that are equidistant from the nominal day, the later record will be selected.
  - If there is more than 1 record on the selected day, the average will be taken, unless otherwise specified.

If multiple, valid nonmissing, categorical measurements exist in an analysis window, records will be chosen based on the following rules if a single value is needed:

- For baseline, the last available record on or prior to the date of the first dose of study drug will be selected. If there are multiple records with the same time or no time recorded on the same day, the value with the lowest severity will be selected (eg, normal will be selected over abnormal for safety electrocardiogram [ECG] findings).
- For postbaseline visits, if there are multiple records with the same time or no time recorded on the same day, the value with the worst severity within the window will be selected (eg, abnormal will be selected over normal for safety ECG findings).

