## 6.1. Secondary Efficacy Endpoints:

- Number (%) of subjects who die by Study Day 28 and by Weeks 8, 12, and 24
- Number (%) of subjects receiving a liver transplant by Study Day 28 and by Weeks 8, 12, and 24
- Summary of Lille score by visit through Week 4
- Number (%) of subjects with Lille response (score < 0.45) at Day 7 (eg, Week 1)
- Number (%) of subjects with Lille null response (score  $\ge 0.56$ ) at Day 7 (eg, Week 1)
- Mortality Risk at Months 2 and 6 based on Lille score response at Day 7 (eg, Week 1) and the baseline MELD score (continuous)
- Number (%) of subjects with infection while on study
- Number (%) of subjects with HRS while on study
- Length of initial hospital stay
- Change from baseline in liver biochemistry tests (ALT, AST, GGT, albumin, alkaline phosphatase, total bilirubin, direct bilirubin, and INR) by analysis visit through Week 24
- Change from baseline in prognostic indices (MELD, CPT, and Maddrey's DF) by analysis visit through Week 24

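### The SAP's Week 1 window lets a Study Day 2 or 3 bilirubin stand as the "Day 7" Lille input when no closer sample exists, so some early stoppers count as observed instead of missing

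*SAP*

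**What the plan says.** **Formula.** SAP 6.2.4 gives the Lille score as a function of age, baseline laboratory values and the bilirubin change from baseline to Day 7, weighted 0.28215 per mg/dL. It has no term for the day of the draw. The bilirubin is chosen "by selecting the total bilirubin value for the subject and visit using the analysis visit windows specified in Section 3.8.2 of this SAP".

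**Analysis window.** Table 3-1 in SAP 3.8.2 sets Week 1 for Lille scores as "2 \leq $ Study Day $\leq 10" (Study Days 2 to 10). If a window holds several records, SAP 3.8.3 selects as follows: "The record closest to the nominal day (nominal day for Week" X being 7 times X, so Day 7 for Week 1. Ties go to the later record.

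**Endpoints.** SAP 6.1 lists "Number (%) of subjects with Lille null response (score $\ge 0.56$ ) at Day 7 (eg, Week 1"), and response (< 0.45) with the same label. SAP 6.2.5 puts the Week 1 score into the Lille-MELD mortality risk. Under SAP 6.2.4 a subject with no score in the window is a failure. A subject who stopped both drugs before Study Day 7 is tabulated by discontinuation reason only if no score exists.

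**Protocol.** Section 6.9.12 has the score "calculated at Day 7 using local laboratory results from Baseline/Day 1 (albumin, total bilirubin, creatinine, PT) and Week 1 (total bilirubin"), and the section "6.3.1. Week 1 Visit (±3 Days") sets the visit window. On treatment, 6.3.1 says "If Lille score is ≥ 0.56 (null response), prednisolone treatment should be held", and 6.9.12 says "Prednisolone should be discontinued in subjects with a Lille Score ≥ 0.56 at Day 7 (null response").

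**The concern.** The analysis window opens two days before the protocol's own visit window, and no earliest valid day is set for a score reported as Day 7. The protocol creates opportunities for such samples. A subject who stops treatment is to have an end-of-treatment visit as soon as possible (6.3.4), which includes chemistry. A subject who stops both drugs before Week 2 then goes to the 30-day and post-treatment visits (3.2), so a sample nearer Day 7 may never be drawn. Unscheduled visits (6.6) also collect chemistry.

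If the only such sample falls on Day 2 or 3, the subject leaves the missing category and gets an observed Lille category based on one or two days of change. A subject who died or stopped before Day 7 could even be counted as a Day 7 responder. The endpoints affected are Lille response and null response (the two with Fisher tests at Week 1), the continuous Week 1 score and the 2- and 6-month mortality risk. These are secondary endpoints; the primary endpoint is safety.

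**Working it through.** **1. The plan's own example.** SAP 6.2.5, with Lille 0.45 and MELD 21:
S = [2.4778 × (0.45 − 0.4114) + 0.0695 × (21 − 24.6812)] × 0.9836 = −0.1576.
2-month risk = 1 − 0.8239^exp(S) = 15.3%; 6-month risk = 1 − 0.7285^exp(S) = 23.7%. Both match the SAP.

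**2. Share of the change captured.** Assume bilirubin changes linearly from Day 1. The share of the Day 7 change reached on day d is (d − 1)/6: 1/6 on Day 2, 1/3 on Day 3, 1/2 on Day 4 and 9/6 on Day 10.

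**3. Distance between cut-offs.** Lille = 1/(1 + exp(R)), so 0.45 is R = ln(0.55/0.45) = 0.2007 and 0.56 is R = ln(0.44/0.56) = −0.2412. The gap is 0.4418/0.28215 = 1.57 mg/dL of bilirubin. A responder on Day 7 reads as null on day d only if the Day 7 fall exceeds 1.57/[1 − (d − 1)/6]:

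| Draw day | Day 7 fall needed (mg/dL) |
|---|---|
| 2 | 1.88 |
| 3 | 2.35 |
| 4 | 3.13 |

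A subject between 0.45 and 0.56 on Day 7 can cross 0.56 with a smaller fall.

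**4. Two illustrative subjects** (all values assumed; no renal insufficiency). R = 3.19 − 0.101 × age + 1.47 × albumin + 0.28215 × fall − 0.11115 × baseline bilirubin − 0.0096 × PT.

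*Falling:* age 50, albumin 2.3 g/dL, bilirubin 20 mg/dL, PT 18 s, Day 7 fall 4 mg/dL. With no change, R = 3.19 − 5.05 + 3.381 − 2.223 − 0.1728 = −0.8748.

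*Rising:* age 50, albumin 2.5 g/dL, bilirubin 14 mg/dL, PT 16.3 s, Day 7 rise 3 mg/dL. With no change, R = 3.19 − 5.05 + 3.675 − 1.5561 − 0.1565 = 0.1024.

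| Draw day | Falling: R | Falling: Lille | Rising: R | Rising: Lille |
|---|---|---|---|---|
| 2 | −0.8748 + 0.1881 = −0.6867 | 0.665 (null) | 0.1024 − 0.1411 = −0.0387 | 0.510 (not null) |
| 3 | −0.8748 + 0.3762 = −0.4986 | 0.622 (null) | 0.1024 − 0.2822 = −0.1797 | 0.545 (not null) |
| 4 | −0.8748 + 0.5643 = −0.3105 | 0.577 (null) | 0.1024 − 0.4232 = −0.3208 | 0.580 (null) |
| 7 | −0.8748 + 1.1286 = 0.2538 | 0.437 (responder) | 0.1024 − 0.8465 = −0.7440 | 0.678 (null) |

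The early draw makes the first subject look worse and the second look better. With MELD 21, the first subject's S is −0.1893 on the Day 7 score, 0.1519 on Day 4 and 0.3664 on Day 2. The 2-month risks are 14.8%, 20.2% and 24.4%.

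**5. How often.** The documents give no sampling days or bilirubin slopes, so this rests on a simulated population (assumed: mean age 48, mean albumin 2.6 g/dL, median bilirubin 14 mg/dL, mean Day 7 fall 0 to 3 mg/dL with SD 3). The ranges are over that mean fall and apply if **every** subject were drawn on the stated day:

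| Shift | Drawn Day 2 | Drawn Day 4 |
|---|---|---|
| Day 7 responder (< 0.45) reads null | 4.3% to 10.7% | 1.0% to 3.0% |
| Any Day 7 score < 0.56 reads null | 8.7% to 16.3% | 4.7% to 8.4% |
| Day 7 null reads < 0.56 | 7.4% to 19.7% | 4.4% to 11.7% |

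For a draw on Day 10, 5.7% to 18.8% of Day 7 null responders read < 0.56.

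**The case against.** **The closest-to-Day-7 rule does most of the work.** This stands for anyone with a later record in the window. It does not help a subject whose only record is from Day 2 or 3.

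**Lille is also summarised at later visits.** This stands in part. The Week 4 LOCF summary carries forward the last score from Study Days 2 to 24, so an early stopper with a single Day 2 sample brings the same value there. The planned listing of scores would let a reader look at single subjects, but the plan has no summary of draw day by arm.

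**A reader might infer that Day 2 samples take responders off prednisolone.** The documents do not support this. Table 3-1 governs analysis only. The treatment rule follows the protocol's Week 1 visit, for which Day 4 is the earliest in-window day.

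**A reader might infer that protocol 6.3.1 and 6.9.12 contradict each other.** That goes too far. Section 6.9.12 itself names the Week 1 bilirubin, and Day 7 reads naturally as that visit's nominal day. The wording is loose and should be reconciled.

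**A reader might infer a bias against one arm.** Nothing in the documents shows sampling that differs by arm. Both arms are blinded and share one window, and the errors run both ways.

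**Study day is not steroid day.** Systemic corticosteroids may start up to 3 days before Day 1, so Study Day 4 can be about Day 7 of steroid for some subjects. This is fair, but the SAP formula counts from the study baseline.

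**Conclusion.** The point holds as a gap in the analysis rules. A Study Day 2 or 3 bilirubin can stand as an observed Day 7 Lille result when no closer record exists, and it displaces the missing-as-failure rule for that subject. The score is then driven mainly by baseline factors and can misclassify in either direction, so the likely effect is dilution. Differential bias would require early stopping or early sampling to differ between arms.

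Draws on Days 4 to 6 are within the protocol window and can also move a score across 0.45 or 0.56. A direct responder-to-null move on Day 4 needs a Day 7 fall above about 3.1 mg/dL and is probably uncommon.

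The number of subjects affected cannot be found from the documents and is probably small. The thresholds rest on linear bilirubin change, and the frequencies on an assumed population. Days 4 to 10 as the protocol window rests on Week 1 meaning Day 7, as SAP 3.8.3 sets it.

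**What to change.** - **Sensitivity analysis (SAP 3.8.2, 6.2.4 and 6.2.5).** Repeat the Day 7 Lille endpoints and the Lille-MELD risk using only bilirubin drawn on Study Days 4 to 10. Apply the same limit to local values substituted under SAP 3.6.1. Subjects sampled only on Day 2 or 3 become missing: failures for the categorical endpoints under the existing rule, and left out of the continuous score and the mortality risk, for which no other imputation is given.
- **Draw day.** Tabulate the actual Study Day of the Week 1 bilirubin by arm.
- **Label.** SAP 2.3 shows that treatment was already unblinded for the primary analysis, so state that this analysis was added afterwards.
- **Interpolation.** Leave out interpolation to Day 7, or keep it only as a secondary check. It leans on Week 2 values that may follow a prednisolone hold.
- **Protocol wording.** The sponsor should reconcile Day 7 in 6.9.12 and 7.5 with the Week 1 ±3-day visit in 6.3.1. No clinical rule is proposed here.

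The cost is one extra derivation and one table from data already collected. The drawback is that a few more subjects count as missing, and so as failures, in the added analysis.

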# 1.2. Study Design

This is a Phase 2, randomized, double-blind, proof-of-concept study evaluating the safety, tolerability, and biological activity of selonsertib in combination with prednisolone versus prednisolone alone in subjects with severe, histologically-confirmed AH. Subjects are 18 to 70 years of age, with a history of excessive alcohol consumption (average of > 40 g/day of alcohol for women and > 50 g/day of alcohol for men); AST  $\geq$  50 and  $\leq$  400 U/L; ALT  $\leq$  300 U/L; AST/ALT ratio  $\geq$  1.5; onset of jaundice within the past 3 months; a screening Maddrey DF score  $\geq$  32 and  $\leq$  60; and a MELD score  $\leq$  30. Subjects consented under Amendment 1 of the study protocol will qualify for the study and be stratified based on the screening MELD score calculated using central laboratory results while all other subjects will qualify for the study and be stratified based on the screening MELD score calculated using local laboratory results. All analyses of laboratory values for efficacy and safety will be based on central laboratory (ie, Covance Laboratories, Inc.) results except for the specific cases for Lille and MELD scores described in Section 3.6.1.

Up to 120 subjects will be randomized to obtain 100 subjects with histologically-proven severe AH who are evaluable for the Full Analysis Set (FAS). Subjects meeting the study's entry criteria will be randomly assigned within strata (screening MELD < 25 or  $\geq$  25) to one of the following 2 treatment groups in a 1:1 ratio:

- Group A (n = 50-60): Selonsertib 18 mg QD + Prednisolone 40 mg QD for 28 days
- Group B (n = 50-60): Selonsertib Placebo QD + Prednisolone 40 mg QD for 28 days

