#### 1.3. Sample Size and Power

The number of subjects was chosen based on clinical experience with other similar proof of concept studies. PPD

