# 3. GENERAL CONSIDERATIONS FOR DATA ANALYSES

Analysis results will be presented using descriptive statistics. For categorical variables, the number and percentage of subjects in each category will be presented; for continuous variables, the number of subjects (n), mean, standard deviation (SD), median, first quartile (Q1), third quartile (Q3), minimum, and maximum will be presented.

All statistical tests (PPD ) will be 2-sided and performed at the 5% significance level unless otherwise specified.

By-subject listings will be presented for all subjects in the Safety Analysis Set unless otherwise specified. Listings will be sorted by subject ID number, visit date, and time (if applicable). Data collected on log forms, such as AEs, will be presented in chronological order within the subject. The treatment group to which subjects were randomized will be used in the listings. Age, sex at birth, race, and ethnicity will be included in the listings, as space permits.

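### The only visible Week 1 Lille test ignores the baseline values built into the score; an analysis adjusted for them should be added as supportive

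*SAP*

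**What the plan says.** SAP 6.2.4 defines the score as a logistic function of a linear predictor R. On its inputs it says "The Lille score is calculated using baseline factors: age, albumin, total bilirubin, serum creatinine, prothrombin time", followed by the change in bilirubin from baseline to Day 7. Two binary endpoints are taken from it at Week 1: response, "defined as a Lille score < 0.45 (yes or no", and null response, a score of 0.56 or more. SAP 6.1 lists both as secondary efficacy endpoints. For these, "p-values from a 2-sided Fisher's exact test will be presented for the Week 1 visit to explore whether" the arms differ. SAP 3 says visible tests "will be 2-sided and performed at the 5% significance level unless otherwise specified". A missing Week 1 score counts as a failure.

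The continuous score at Weeks 1 to 4 (SAP 6.2.4) and bilirubin value, change and percentage change by visit (SAP 6.2.8) are summarised by arm, with no test or adjusted estimate visible.

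On size, SAP 1.2 says "Up to 120 subjects will be randomized to obtain 100 subjects with histologically-proven severe AH who are evaluable for the Full Analysis Set (FAS", with subjects assigned to "treatment groups in a 1:1 ratio". SAP 1.3 says "The number of subjects was chosen based on clinical experience with other similar proof of concept studies"; the rest of that section is redacted. No power, effect size or SD for Lille can be read.

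**The concern.** In an observed score, randomised treatment can act only through Day 7 bilirubin. Age, albumin, baseline bilirubin, renal insufficiency and prothrombin time are settled before the first dose, and their joint contribution can be computed exactly from values the score already needs. An unadjusted comparison leaves all that between-subject variation in the error term, and cutting the score at 0.45 or 0.56 discards more information.

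The trial is described as proof-of-concept and as evaluating biological activity. If the one visible p-value on early response has low power, a non-significant result says little about whether the drug changed bilirubin. With about 50 per arm, a chance imbalance in age or albumin could also hide an effect or imitate one.

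**Working it through.** **No plan figure to reproduce.** The visible text gives no power for this test. As a check on reading the SAP's formulas, its worked mortality-risk example (SAP 6.2.5) does reproduce: S = −0.1576, 15.3% and 23.7%.

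**Splitting the score.** From SAP 6.2.4, R = R0 + 0.28215 × (baseline − Day 7 bilirubin), where

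R0 = 3.19 − 0.101·age + 1.47·albumin − 0.206·renal insufficiency − 0.11115·baseline bilirubin − 0.0096·PT.

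The score is exp(−R)/[1 + exp(−R)], so R is minus its logit and a higher R is better.

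**Weight of the baseline inputs**, as mg/dL of Day 7 bilirubin change (coefficient × difference ÷ 0.28215):
- 10 years of age: 1.01 ÷ 0.28215 = 3.6
- 0.5 g/dL albumin: 0.735 ÷ 0.28215 = 2.6
- 5 mg/dL baseline bilirubin: 0.55575 ÷ 0.28215 = 2.0
- renal insufficiency: 0.206 ÷ 0.28215 = 0.7
- 5 s of PT: 0.048 ÷ 0.28215 = 0.2

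**Assumptions.** The documents give no SDs. Centres are the SAP 3.4 subgroup cut-points treated as medians: age 50, bilirubin 14 mg/dL, PT 16.3 s, albumin 3.0 (printed as mg/dL, read as g/dL), with albumin 2.5 as a sensitivity case. Assumed SDs for age, albumin, baseline bilirubin and bilirubin change are 10, 0.5, 7, 4.5 (central); 8, 0.4, 5, 6 (narrow baseline, wide change); 11, 0.6, 8, 3 (wide baseline, narrow change). PT SD is 2 s. A fourth setting is central with change depending on baseline (slope −0.2).

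**Baseline share of the variance of R**, by hand and ignoring the small PT and renal terms:
- Central: baseline 1.01² + 0.735² + 0.778² = 2.17; change (0.28215 × 4.5)² = 1.61; share 2.17/3.78 = 57%.
- Narrow baseline: 1.31/(1.31 + 2.87) = 31%.
- Wide baseline: 2.80/(2.80 + 0.72) = 80%.

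Simulation gives 58%, 33% and 80%, and 55% with the slope.

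**Power.** 4,000 simulated trials per case, 50 per arm, two-sided 5%, no missing scores. Effects were set so that an adjusted bilirubin analysis has about 80% or 90% power; in the central case, (1.960 + 0.842) × 4.5 × √(2/50) = 2.52 mg/dL. Ranges cover the two albumin centres.

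| Setting | Effect (mg/dL) | ANCOVA of R on R0 | Unadjusted t-test on R | Fisher 0.45 | Fisher 0.56 |
|---|---|---|---|---|---|
| Central | 2.52 | 77–79% | 43% | 19–23% | 16–22% |
| Central | 2.92 | 89% | 53% | 26–30% | 21–27% |
| Narrow baseline | 3.36 | 77% | 60–61% | 31–35% | 25–31% |
| Narrow baseline | 3.89 | 87–88% | 73–75% | 38–45% | 31–41% |
| Wide baseline | 1.68 | 78% | 24% | 10–13% | 8–12% |
| Wide baseline | 1.94 | 89% | 30–31% | 14–17% | 11–14% |
| Central, slope −0.2 | 2.52 | 73–75% | 47–48% | 21–25% | 16–23% |
| Central, slope −0.2 | 2.92 | 86–87% | 59–61% | 27–34% | 20–31% |

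For effects set at about 80% the Fisher range at 0.45 is 10–35%; for about 90% it is 14–45%. Relative loss at 0.45 runs from 48% (1 − 0.453/0.868) to 87% (1 − 0.101/0.783).

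**Where the loss arises (central, 2.52 mg/dL, albumin 3.0).** The effect on R is 0.28215 × 2.52 = 0.711.
- Adjusted: 0.711/(1.27 × 0.2) = 2.80, power about 80%.
- Unadjusted: 0.711/(1.94 × 0.2) = 1.83, about 45% (simulated 43%).
- Dichotomised: response moves from 70.7% to 81.9%. A normal approximation gives about 26%; Fisher gives 19%.
- Exact enumeration puts Fisher's true size at 3.5% for a 50% response rate and 3.0% for 65%.

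In the narrow-baseline setting (3.36 mg/dL), ignoring R0 costs about 16 points and dichotomising with Fisher about 26–30, so the split between causes also depends on the assumed SDs.

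**Second parameterisation.** Here the effect is a proportional lowering of Day 7 bilirubin, with other assumed SDs. For a further 14%, repeated runs gave Fisher 16–20% against ANCOVA 46–76%; for 22%, 36–45% against 84–99%. ANCOVA rejected 4–6% of the time under the null in the most recent run.

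**The case against.** **Role of the test.** It is worded as exploratory, on one of many secondary endpoints, in a trial whose primary endpoint is safety. This stands, and it limits the importance of the point.

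**Other coverage.** Bilirubin change is reported by visit and plotted, Lille is summarised as a continuous score, baseline tables are shown by arm, and SAP 3.4 breaks Week 1 Lille categories down by age, bilirubin, PT, albumin and creatinine. An imbalance would therefore be visible. But these summaries are descriptive and give no adjusted treatment estimate.

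**Visibility.** Text about tests in SAP 3 is redacted and SAP 3.5 is blank, so another test cannot be excluded. The claim is limited to what can be read.

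**Adjusting the binary endpoint gains less.** In one set of runs an unadjusted likelihood-ratio test closed 47–68% of the gap between Fisher and the R0-adjusted logistic model; in one case power was 29% (Fisher), 45% (unadjusted) and 55% (adjusted). With an assumed 10% of scores missing and counted as failures, the adjusted logistic model gained only 5–19 points over Fisher across runs. This stands, and is why the main addition should be the continuous analysis.

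**Missing scores.** Because a missing score is a failure, early death or dropout can also move the binary endpoint, and ANCOVA of R would leave those subjects out. True; the two analyses answer different questions. With 10% missing at random, ANCOVA on observed scores still had 44–67% power against 12–15% for Fisher (14% effect).

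**Timing.** This SAP governs the final analysis (SAP 1). Treatment assignments had already been unblinded for the primary analysis (SAP 2.3), and SAP 6.5 reports no evidence of better efficacy at that point. Replacing the test now would be a change made after unblinding. This stands and decides the form of the fix.

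**Conclusion.** The concern holds in a limited form. The only visible Week 1 Lille inference is an unadjusted Fisher test on a dichotomised score whose inputs, apart from Day 7 bilirubin, are all baseline values. Against a baseline-adjusted continuous analysis, roughly half or more of the power is lost in every case run. The size rests on assumed SDs, 50 per arm, cut-points taken as medians and, in the main table, no missing scores.

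A reader might infer three stronger things that the documents do not support:
- That half of the score is baseline by formula. The formula gives coefficients, not variance shares.
- That most of the power is lost whatever the comparator. Against an adjusted logistic model of the same binary endpoint the loss is nearer 40% (for example 16–20% against 28–38%), and part of that is Fisher's conservatism.
- That a design claim fails, or that Lille is the trial's main activity readout. No efficacy power is visible, and no section gives Lille that rank.

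**What to change.** Keep the Fisher tests as planned and add the following to SAP 6.2.4:

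- Compute R and R0 for each subject directly from the formula inputs, using the laboratory source that SAP 3.6.1 assigns to that subject. Do not back-calculate R from the score rounded to 0.001.
- Fit an ANCOVA of Week 1 R on arm and R0 in the FAS and mITT, among subjects with an observed Week 1 score. Report the adjusted difference and its 95% CI.
- Report the number of missing Week 1 scores, with reasons, by arm beside it.
- Optionally, fit logistic models of response and of null response on arm and R0, with missing counted as failure.
- Label all of these as supportive and added after unblinding for the primary analysis.

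The cost is a small amount of programming and no new data. The results have post hoc status, the ANCOVA excludes subjects without a Week 1 score, and the optional logistic test can be slightly liberal at this sample size (null rejection about 4–7% in the runs).
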